Amendment 05/ Version #13/ May 30, 2023
Amendment 06/Version #14/January 3, 2025

SCHEMA

*Within each cohort, we will employ an optimal Simon two-stage design. Specifically, within each cohort, we will enroll 9 patients, and if 0 respond, the study will be stopped early for futility within that cohort. Otherwise, an additional 18 patients will be enrolled, and if there are 4 or more responses out of the total sample of 27 patients, we will conclude that the treatment is worthy of further consideration within that cohort. This design has an overall type-I error rate of 5% (one-sided) within each cohort, and provides 88% power to reject the null hypothesis that the response rate is 0.05 when the true response rate is 0.25. Within a given cohort, this design has a 63% chance of stopping early and an expected total enrollment of 15.7 patients under the null hypothesis (i.e. if the true response rate were 0.05).

The Recommended Phase 2 dose for Telaglenastat (CB-839) HCl monotherapy is 800 mg BID. We will use this as the starting dose for this Basket trial. If patient develops toxicity then the dose can be reduced as per table below:

Dose Reductions of Telaglenastat (CB-839) HCl	
Dose Level	Telaglenastat (CB-839) HCl Dose
Starting dose	800 mg BID
First dose reduction	600 mg BID
Second dose reduction	400 mg BID
Third dose reduction	Discontinue Telaglenastat (CB-839) HCl

TABLE OF CONTENTS

TITLE PAGE

SCHEMA.....	4
TABLE OF CONTENTS.....	5
1. OBJECTIVES.....	8
1.1 Primary Objectives.....	8
1.2 Secondary Objectives.....	8
1.3 Exploratory objectives:	8
2. BACKGROUND	8
2.1 Study Disease(s).....	8
2.2 Telaglenastat (CB-839) HCl	10
2.3 Rationale	13
2.4 Correlative Studies Background	18
3. PATIENT SELECTION	23
3.1 Eligibility Criteria	23
3.2 Exclusion Criteria	24
3.3 Inclusion of Women and Minorities	25
4. REGISTRATION PROCEDURES	25
4.1 Investigator and Research Associate Registration with CTEP	26
4.2 Site Registration.....	28
4.3 Patient Registration.....	29
4.4 General Guidelines.....	30
5. BIOMARKER, CORRELATIVE, AND SPECIAL STUDIES.....	31
5.1 Summary Table for Specimen Collection.....	31
5.2 Specimen Procurement Kits and Scheduling	32
5.3 Specimen Tracking System Instructions.....	33
5.4 Specimen Collection	36
5.5 Shipping Specimens from Clinical Site to the EET Biobank	39
5.6 Shipping to the Mayo Clinic Cancer Center Pharmacology Shared Resource.....	41
5.7 Biomarker Plan	42
5.8 Integrated Correlative Studies.....	44

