1.2 Secondary Objectives

- 1.2.1 To determine the safety, PFS, TTP and OS.
- 1.2.2 To determine the ORR (highest objective response achieved between start of therapy and progression), TTR and CBR of Telaglenastat (CB-839) HCl
- 1.2.3 Correlative Objectives: To assess pharmacodynamic changes and adaptive responses and correlate with response to treatment as well as disease progression

1.3 Exploratory objectives:

- 1.3.1 Correlate ¹⁸F-FDG PET/CT pre-therapy and 8-weeks post-therapy response to Telaglenastat (CB-839) HCl therapy
- 1.3.2 Evaluate changes in level of circulating tumor DNA at baseline, one month on-treatment and time of progression (MoCHA Labs) to treatment response.
- 1.3.3 Quantify the peripheral blood concentrations of the metabolites: Aspartate, Glutamate, Glutamine and Arginine (@Mayo clinic Oncometabolomics core) and correlate with response.
- 1.3.4 Evaluate the PD effect of Telaglenastat (CB-839) HCl on systemic levels of the TCA cycle metabolites in peripheral blood (baseline and one month) as part of the protocol.
- 1.3.5 Evaluate tumor by Reverse phase protein array (@core facility at MD Anderson) and RNA seq to evaluate changes from pre-treatment, during treatment and post treatment specimens.
- 1.3.6 Perform PDX modelling-co-clinical trials (@[name] lab MD Anderson) to understand response / resistance mechanisms and also evaluate combination therapies for future development.

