2.3 Rationale

There is an unmet therapeutic need for advanced-stage cancer patients with *NF1* mutant malignant peripheral nerve sheath tumor (MPNST), *NF1* mutant cancers, *KEAP1/NRF2* & *STK11/LKB1* pathway aberrant tumors. To fill the therapeutic needs, we propose a basket clinical trial with Telaglenastat (CB-839) HCl (NSC# 795998), a potent and selective reversible inhibitor of glutaminase-1 activity. It follows that the new experimental therapeutic agent Telaglenastat (CB-839) HCl acts as an allosteric and noncompetitive inhibitor of both splice variants of the broadly expressed glutaminase-1 (gene symbol: GLS, selectivity $\sim 0.028 \mu\text{M} \pm 0.007$), but does not inhibit glutaminase-2 (GLS2, selectivity $>1000 \mu\text{M}$), which is the variant predominantly found in the human liver. Telaglenastat (CB-839) HCl has antineoplastic and has pro-apoptotic activity in a variety of human tumor cell lines, including triple-negative breast cancer (TNBC), clear cell renal cell carcinoma (RCC), and mesothelioma, as well as hematological cell lines of relapsed or refractory leukemia, multiple myeloma (MM) and non-Hodgkin's lymphoma (NHL). Among 24 non-small cell lung cancer cell lines, 11 (46%) of 24 cell lines showed substantial and significant 72-hour $1 \mu\text{M}$ Telaglenastat (CB-839) HCl monotherapy cytotoxicity. Unpublished phase 1 studies of orally-administered Telaglenastat (CB-839) HCl monotherapy have found so far that the agent is well tolerated, has no maximum tolerated dose (MTD) identified, and has a 600 mg twice daily (BID) with food for a recommended Phase II dose. Known pharmacology data are presented in Table 1. Pharmacodynamic studies in the phase 1 trials show an up to 96% reduction in patient tumor glutaminase-1 activity after a 21-day Telaglenastat (CB-839) HCl drug exposure(18). Telaglenastat (CB-839) HCl monotherapy provides minimal (<5%) clinical activity in phase I trials. As such, investigators and Calithera Biosciences, Inc. seek Telaglenastat (CB-839) HCl-agent trials with NCI CTEP. In prior work, Calithera Biosciences, Inc. has determined tumor GLS activity and blood or tumor levels of glutamine, glutamate, and aspartate after Telaglenastat (CB-839) HCl drug exposure. Inhibition of GLS activity in tumor confirms desired pharmacodynamic effect of Telaglenastat (CB-839) HCl (Fig. 2). Tandem mass spectroscopy studies of tumor or of blood samples have shown (a) desired rise in glutamine levels after Telaglenastat (CB-839) HCl, (b) fall in glutamate levels after Telaglenastat (CB-839) HCl, and (c) fall in Krebs cycle downstream aspartate levels.

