2.4.8 Transcriptional Profiling of RNA

We hypothesize that RNA expression signature of tumor tissue collected at baseline, during treatment and upon progression may predict clinical benefit from targeted therapies. RNA expression signature will be assessed when samples are available from responders as well as non-responders to allow for comparison.

Tissue will be macrodissected and total RNA isolated using a Qiagen protocol. An Illumina sequencing library will be generated using an Illumina RNA Exome library preparation kit. Samples will be sequenced on an Illumina NovaSeq instrument, yielding approximately 7 million reads per sample. Sequencing reads will be matched to a collection of human transcripts. Logarithm of the normalized number of the matching reads will be used as a measure of the corresponding gene expression. Only genes with large enough counts of matching reads will be used in the analysis. We estimate that about 15,000 genes will be analyzed.

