9.3 Analysis of Secondary Endpoints

Secondary Endpoint:

1. Safety, progression free survival (PFS), time to progression (TTP) and overall survival (OS).

We will tabulate toxicity by cohort, type, severity and attribution. For patients with objectively measurable disease, as defined by RECIST v1.1, progression-free survival (PFS), time to progression (TTP), and overall survival (OS) will be calculated. We will estimate PFS and OS using the Kaplan-Meier method with time zero set to C1D1. OS is defined as time to death from any cause and PFS is defined as time to progression or death whichever comes first. OS is censored in patients not known to be dead at the time they were last known to be alive and PFS is censored in patients alive and progression-free at the date of last clinical follow-up. We will estimate the medians and select probabilities along with 95% confidence intervals. TTP will be estimated in a similar fashion and is defined as time to progression starting at C1D1. If more than a handful of patients die without progression, we will use Aalen-Johansen estimates to adjust for the competing risk of death.

2. Overall response rate and clinical benefit rate (CR, PR and SD > 12 weeks of Telaglenastat (CB-839) HCl)

Ho: CB 839 - Response Rate (RR) in disease	Ha: Target RR of combination in disease	Calculation	Statistic & Significance	Responsible investigator
5 %	25 %	ORR = pre-therapy sum longest diameters (5 or less lesions) / post-therapy sum longest diameters (same 5 or less lesions)	It is a one-sample binomial test with alpha = 5%.	[name]

3. Pharmacodynamic tumor oncometabolite levels of glutamine, glutamate, and aspartate between 0 and 8 hours post- Telaglenastat (CB-839) HCl dose among patients with persistent or recurrent metastatic cancers.

We will assess PD changes before and after treatment using the Wilcoxon signed rank test. For normally distributed data, with 27 patients we can detect a standardized mean difference (mean difference divided by standard deviation of differences) = 0.6 with 85% power assuming a two-sided 5% alpha. We will correlate these changes with response to treatment using Wilcoxon rank sum test. We will also perform a ROC curve analysis. With 27 patients, if the response rate is roughly 50%, we can detect an area under the ROC curve = 0.83 as significantly higher than 0.5 (the null value) with 85% power assuming a 5% alpha.

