Target lesions. All measurable lesions up to a maximum of 2 lesions per organ and 5 lesions in total, representative of all involved organs, should be identified as **target lesions** and recorded and measured at baseline. Target lesions should be selected on the basis of their size (lesions with the longest diameter), be representative of all involved organs, but in addition should be those that lend themselves to reproducible repeated measurements. It may be the case that, on occasion, the largest lesion does not lend itself to reproducible measurement in which circumstance the next largest lesion which can be measured reproducibly should be selected. A sum of the diameters (longest for non-nodal lesions, short axis for nodal lesions) for all target lesions will be calculated and reported as the baseline sum diameters. If lymph nodes are to be included in the sum, then only the short axis is added into the sum. The baseline sum diameters will be used as reference to further characterize any objective tumor regression in the measurable dimension of the disease.

Non-target lesions. All other lesions (or sites of disease) including any measurable lesions over and above the 5 target lesions should be identified as **non-target lesions** and should also be recorded at baseline. Measurements of these lesions are not required, but the presence, absence, or in rare cases unequivocal progression of each should be noted throughout follow-up.

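### Section 9.3 relates metabolite change to tumour response only through a two-group test and ROC curve, although tumour size is recorded on a continuous scale that keeps more power and needs no responders

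*Combined protocol and SAP*

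**What the plan says.** Secondary objective 1.2.3 is "To assess pharmacodynamic changes and adaptive responses and correlate with response to treatment as well as disease progression". For response, Section 9.3 item 3 gives two methods: "We will correlate these changes with response to treatment using Wilcoxon rank sum test", and a ROC curve. The power statement for 27 patients is that "if the response rate is roughly 50%, we can detect an area under the ROC curve = 0.83 as significantly higher than 0.5", "with 85% power assuming a 5% alpha". Separately, the same item tests before-to-after metabolite change with a signed-rank test.

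The cohort rule in the Schema and Section 9.1 is that "we will enroll 9 patients, and if 0 respond, the study will be stopped early for futility within that cohort".

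On tumour size, Section 12.1.2 says "A sum of the diameters (longest for non-nodal lesions, short axis for nodal lesions) for all target lesions will be calculated" at baseline. The Section 11 calendar repeats the measurements every 8 weeks for the first 13 cycles. (Section 12.1 gives a 12-week interval; the two should be reconciled, but this point holds under either.) Measurable disease is an entry criterion (3.1.8, 3.1.9).

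Item 3 does not define response, does not say whether the analysis is per cohort or pooled, and has no rule for a cohort without responders. No analysis sets metabolite change against continuous tumour change.

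**The concern.** A rank-sum test and a ROC curve reduce each patient's tumour outcome to yes or no. RECIST categories are needed for the response endpoint, but nothing in the plan requires them for a biomarker association, and the finer measure is collected anyway.

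The split also sits badly with the design. On a per-cohort CR/PR reading, a cohort stops at stage 1 exactly when it has no responder group. Few responders is a realistic case: 5% is the null rate in Section 9.1, and Section 2.3 says "Telaglenastat (CB-839) HCl monotherapy provides minimal (<5%) clinical activity in phase I trials". At stake is whether the trial can say if stronger target inhibition goes with better tumour control, most of all where responses are scarce.

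**Working it through.** **1. The plan's own figure.** Noether's formula for the rank-sum test, two-sided 5%, with responder share c: power = Φ(√(12·N·c·(1−c))·(AUC−0.5) − 1.96). With N=27, c=0.5 and AUC 0.83 this is Φ(9×0.33 − 1.96) = Φ(1.01) = 84.4%. The N=20 (AUC 0.887) and N=15 (AUC 0.947) figures give 85.0% and 85.1%. The stated 85% reproduces.

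**2. When the comparison cannot be made** (CR/PR, one cohort).
- No responders at stage 1: 0.95⁹ = 0.630 at a 5% rate; 0.75⁹ = 0.075 at 25%.
- One responder in 27: smallest two-sided exact p = 2/27 = 0.074. With two responders it is 2/351 = 0.006.
- Cohort ends with at most one responder, 5% rate: 0.630 + 9×0.05×0.95⁸×0.95¹⁸ = 0.630 + 0.119 = 0.749.

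**3. Assumed strength of association.** The documents give no correlation between metabolite change and tumour change. Assume bivariate normality. For a median split, AUC = 0.5 + (2/π)·asin(ρ/√2), so AUC 0.83 corresponds to ρ of about 0.70.

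**4. Power at N=27, ρ=0.70** (simulation; Spearman on continuous change against exact rank-sum on the split, two-sided 5%).

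| Responders | Rank-sum | Spearman, all measured | Spearman, worst 30% tied at worst rank |
|---|---|---|---|
| 50% | 89% | 98% (gap 9) | 97% (gap 8) |
| 25% | 80% | 98% (gap 18) | 97% (gap 17) |
| 5% | 23% | 98% (gap 75) | 97% (gap 74) |

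The tied column stands in for patients who progress before a scan. At 15% responders the rank-sum test has 64%, a gap of 34 points with all measured.

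**5. Other correlations, N=27, all measured.** Loss in points at 50% / 25% responders: ρ 0.2, 4/6; 0.3, 9/13; 0.4, 15/21; 0.5, 19/27; 0.6, 17/26; 0.8, 2/7; 0.9, 0/2. The range is about 0 to 27.

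**6. Patients without a follow-up scan, N=27, ρ=0.70.** Suppose 20% stop early for reasons unrelated to the tumour.
- All stoppers given worst rank: Spearman 61-62%, against 65-69% for the rank-sum test with stoppers counted as non-responders. The gain reverses.
- Stoppers left missing: Spearman about 93%. Part of that gap comes from leaving them out. The comparison with both tests at N=20 is 92% against 76% (50% responders) and 64% (25%).

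**7. Inside a cohort stopped at 0/9** (5% rate, worst 30% tied): Spearman can be computed, with power of about 44% at ρ=0.70 and 19% at ρ=0.5.

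**The case against.** The planned test is valid and matches objective 1.2.3; this is about efficiency, not a wrong figure. That stands. Four stronger readings are tempting, and the documents do not support them.

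- *A reader might take 8 to 17 points as a property of the plan.* It rests on an assumed correlation, N=27 and 25-50% responders. The very large gaps come from few responders, which overlaps with the separate question of the 50% assumption. By the formula in step 1, power at AUC 0.83 falls to 73% at 25% responders and 25% at 5%. The loss from splitting is still there at 50%, but is then about 8 or 9 points.
- *A reader might infer that a stopped cohort yields no pharmacodynamic information.* The signed-rank test needs no responders and shows whether metabolites moved. Only the association with response is lost.
- *A reader might take per-cohort CR/PR as the plan's rule.* N=27 matches one full cohort, but item 3 does not say so. Item 2 of the same section names clinical benefit, and Section 2.2.6 reports 46% with stable disease or better, near the assumed 50%. On that definition 0/9 need not empty a group, though at a 46% split the power is still 89% against 98% (ρ=0.70) or 53% against 70% (ρ=0.5). If the four cohorts are pooled, stopped cohorts supply non-responders. At a 25% rate and ρ=0.5 the power is then 96% against 99.8%, so little is lost. At 5% it is 39% against 95%, with a 0.630⁴ = 16% chance of no responder at all.
- *A reader might extend the point to the RNA work,* where Section 2.4.8 says "RNA expression signature will be assessed when samples are available from responders as well as non-responders to allow for comparison". That analysis is exploratory, and objective 1.3.5 looks at change over time without needing responders.

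The strongest objection concerns the remedy. Section 6.3 allows stopping for adverse events, withdrawal, non-compliance or intercurrent illness. Giving all such patients the worst rank can leave Spearman with less power than the planned test (step 6). This stands, and it shapes the fix.

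**Conclusion.** The concern holds as a weakness of efficiency and estimability in a secondary analysis. The only analyses of metabolite change against response need two groups, while a continuous measure is already collected.

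On a per-cohort CR/PR reading, the comparison does not exist in a cohort stopped at 0/9 (63% chance at a 5% rate, 7.5% at 25%), and one responder in 27 cannot give p<0.05. Both results are exact, but depend on a reading that the plan neither states nor excludes.

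The power loss is roughly 8 to 17 points at N=27 with 25-50% responders, assuming bivariate normality and ρ of about 0.70. It is about 0 to 27 points over ρ 0.2-0.9, and larger with fewer responders. The gain from a rank correlation also depends on unscanned patients not all being given the worst rank. The change is worth making because it needs only wording; the trial's primary conclusions are unaffected.

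**What to change.** In Section 9.3 item 3:

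- Add, as the main association analysis, a Spearman rank correlation between metabolite change and best percentage change from baseline in the sum of target-lesion diameters.
- Give the worst rank only to patients who die or progress, objectively or clinically, before a first follow-up scan.
- Treat patients who stop before that scan for other reasons (adverse event, withdrawal, non-compliance) as missing, with a sensitivity analysis that gives them the worst rank.
- Keep the rank-sum test and ROC curve as supportive analyses, run when both groups have at least 2 patients. State which definition of response they use and whether they are per cohort or pooled.

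The cost is wording only: no new data, visits or patients. There are three downsides. Percentage change ignores new and non-target lesions, which is a reason to keep the responder-based analyses. The result depends somewhat on how unscanned patients are handled. Power remains limited in a 9-patient cohort.

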2.4.9 PDX Models

To explore mechanisms of resistance of *NFI*-aberrant tumors to glutaminase inhibition using pre- and post-treatment tumor biopsies obtained from patients treated on a clinical trial of Telaglenastat (CB-839) HCl, and patient-derived xenograft (PDX) models.

CLIA certified molecular profiling is required for study entry. We will enroll patients into the different baskets. The primary end-point is radiographic response. If there are 4 or more responses out of the total sample of 27 patients, we will conclude that the treatment is worthy of further consideration. This optimal Simon two-stage design with a one-sided type-I error rate of 5% provides 88% power to compare a null response rate of 5% and an alternative response rate of 25%. Patients will undergo matched pre- and post-treatment (week 4 and upon progression) biopsies that will be used to elucidate pharmacodynamic changes and adaptive responses by transcriptome and proteomic (RNAseq and RPPA) analyses. These changes will be correlated with response to treatment. The *in vitro* studies will inform the studies performed on these clinical samples. Finally, PDX models will be developed from tumor specimens obtained from patients with treated on this or other studies. These new models will provide an opportunity to test the effects of possible new drug combinations designed to overcome Telaglenastat (CB-839) HCl resistance.

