9. STATISTICAL CONSIDERATIONS

9.1 Study Design/Endpoints

Primary Endpoint:

1. Best overall response rate (BORR) based on RECIST V1.1 achieved by 6 months of CB-839 HCl treatment in specific pathway aberrant tumors (MPNST, NF1, KEAP1/NRF2 & STK11/LKB1)

This will be a basket trial that will enroll patient in four different basket cohorts with specific pathway aberrant tumors.

Cohort (Basket) 1: *NF1* mutant malignant peripheral nerve sheath tumors (MPNST)

Cohort (Basket) 2: *NF1* mutant other cancers

Cohort (Basket) 3: *KEAP1/NRF2* mutant cancers

Cohort (Basket) 4: *STK11/LKB1* mutant cancers

Within each cohort, we will employ an optimal Simon two-stage design. Specifically, within each cohort, *we will enroll 9 patients, and if 0 respond*, the study will be stopped early for futility within that cohort. Otherwise, an additional 18 patients will be enrolled, and if there are 4 or more responses out of the total sample of 27 patients, we will conclude that the treatment is worthy of further consideration within that cohort.

This design has an overall type-I error rate of 5% (one-sided) within each cohort, and provides 88% power to reject the null hypothesis that the response rate is 0.05 when the true response rate is 0.25. Within a given cohort, this design has a 63% chance of stopping early and an expected total enrollment of 15.7 patients under the null hypothesis (i.e. if the true response rate were 0.05).

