9.2 Sample Size/Accrual Rate

We plan to accrue about 108 patients in this study (up to 27 patients per cohort). It is anticipated that 2-4 patients may be enrolled per month onto this study. It is expected that 18-30 months will be required to accrue the number of patients necessary to complete the trial.

PLANNED ENROLLMENT REPORT

Racial Categories	Ethnic Categories				Total
	Not Hispanic or Latino		Hispanic or Latino		
	Female	Male	Female	Male	
American Indian/ Alaska Native	0	0	9	9	18
Asian	5	4	5	4	18

Racial Categories	Ethnic Categories				Total
	Not Hispanic or Latino		Hispanic or Latino		
	Female	Male	Female	Male	
Native Hawaiian or Other Pacific Islander	0	0	0	0	0
Black or African American	9	9	9	9	36
White	9	9	9	9	36
More Than One Race	0	0	0	0	0
Total	23	22	32	31	108

PHS 398 / PHS 2590 (Rev. 08/12 Approved Through 8/31/2015)

OMB No. 0925-0001/0002

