Assuming 20 patients have data, we will have 85% power to detect a standardized effect size of 0.706 using a paired t-test and we can detect an area under the ROC curve of 0.887. Assuming 15 patients have data, we will have 85% power to detect a standardized effect size of 0.832 using a paired t-test and we can detect an area under the ROC curve of 0.947.

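### The 85% power for relating metabolite change to response assumes about 50% responders, while the design rates are 5% and 25%; at AUC 0.83 and n=27, exact power is about 81% with 7 responders and 62% with 4

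*Combined protocol and SAP*

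**What the plan says.** Section 9.3, item 3, plans a signed-rank test of metabolite levels before and after dosing, and then relates the changes to outcome: "We will correlate these changes with response to treatment using Wilcoxon rank sum test", together with an ROC analysis. The power claim for that second step is: "With 27 patients, if the response rate is roughly 50%, we can detect an area under the ROC curve = 0.83", against a null of 0.5, with 85% power and a 5% alpha whose sidedness is not given. For fewer patients with data, the section continues with "we can detect an area under the ROC curve of 0.887" (20 patients) and "we can detect an area under the ROC curve of 0.947" (15 patients), without repeating the assumed share of responders.

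The response rates used everywhere else are much lower. Section 9.1 says the design "provides 88% power to reject the null hypothesis that the response rate is 0.05 when the true response rate is 0.25", and calls the treatment worthy of further study in a cohort "if there are 4 or more responses out of the total sample of 27 patients". Section 9.3, item 2, repeats 5% and 25%. Section 9.2 plans "up to 27 patients per cohort", so the 27 in item 3 matches one full cohort. Section 2.4.9 says: "The primary end-point is radiographic response".

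**The concern.** At a fixed total sample size, a rank-sum comparison is most powerful when the two groups are equal in size, and it loses power as the smaller group shrinks. The 50% assumption is therefore the most favourable one available, and it is twice the rate the trial treats as success. Under the design alternative a full cohort yields about 7 responders (27 × 0.25 = 6.75). Under the null the expected count is 27 × 0.05 = 1.35.

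No section supports 50% for radiographic response. Section 2.3 puts monotherapy activity below 5%. The nearest figure is the 46% with stable disease or better (34 of 74) in section 2.2.6, which is a different outcome and is not linked to item 3.

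What is at stake is interpretation. Objective 1.2.3 lists correlation of pharmacodynamic change with response as secondary (the blood-metabolite correlation in 1.3.3 is exploratory). If a cohort just passes and shows no significant link between metabolite change and response, a reader relying on the stated 85% would give that negative result more weight than it deserves.

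**Working it through.** **Inputs.** From section 9.3, item 3: n = 27, 20 and 15; AUCs 0.83, 0.887 and 0.947; null AUC 0.5; power 85%; alpha 5%. From section 9.1: response rates 5% and 25%, and 4 responses of 27 to pass.

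**Step 1: reproduce the plan's figures.** Noether's rank-sum formula, with c the share of responders, gives the detectable AUC as

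AUC = 0.5 + (z0.975 + z0.85) / √(12·c·(1−c)·n), where z0.975 + z0.85 = 1.960 + 1.036 = 2.996.

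At c = 0.5:
- n = 27: 0.5 + 2.996/√81 = 0.833
- n = 20: 0.5 + 2.996/√60 = 0.887
- n = 15: 0.5 + 2.996/√45 = 0.947

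All three match. One-sided 5% does not: it gives about 91% power at n = 27 and AUC 0.83. The plan's figures are therefore two-sided with equal groups, including those for 20 and 15 patients.

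**Step 2: how likely is a 50:50 split under the design?** At a 25% response rate, the probability of 13 or more responders among 27 is 0.8%.

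**Step 3: power by the plan's own formula at realistic counts.** Power = Φ(√(12·c·(1−c)·n)·(AUC − 0.5) − 1.960), with n = 27 and AUC 0.83:
- c = 0.5: Φ(9.000 × 0.33 − 1.960) = Φ(1.01) = 84%
- 7 of 27: Φ(7.888 × 0.33 − 1.960) = Φ(0.643) = 74%
- 4 of 27: Φ(6.394 × 0.33 − 1.960) = Φ(0.150) = 56%

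**Step 4: exact test.** Noether's formula is approximate, so power was also simulated for the exact two-sided 5% rank-sum test, with critical values from the exact null distribution of U. Data were equal-variance normal with shift √2·Φ⁻¹(AUC), an assumption.

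| n = 27, AUC 0.83: responders / non-responders | Exact power |
|---|---|
| 13 / 14 | 90% |
| 7 / 20 | 81% |
| 6 / 21 | 76–77% |
| 5 / 22 | 70% |
| 4 / 23 | 62% |
| 3 / 24 | 50% |

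Exponential instead of normal data gives 78–83% with 7 responders and 60–63% with 4.

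Averaged over the number of responders in a cohort that reaches stage 2, exact power is 89% at a 50% response rate, 77% at 25%, 61% at 15% and 29% at 5%.

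**Step 5: smaller samples, exact test.** With 20 patients and AUC 0.887, power is 83% with 5 responders and 78% with 4. With 15 patients and AUC 0.947, it is 91% with 4 responders, so that stated figure still holds.

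**Step 6: AUC needed for 85% power, exact test.**

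| Responders / n | AUC needed | Plan states |
|---|---|---|
| 13 / 27 | 0.81 | 0.83 |
| 7 / 27 | 0.845 | 0.83 |
| 4 / 27 | 0.90 | 0.83 |
| 3 / 27 | 0.93 | 0.83 |
| 5 / 20 | 0.89 | 0.887 |
| 4 / 15 | 0.93 | 0.947 |

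**The case against.** The strongest reply is that the statement is true as written. The 50% is an explicit condition, the AUCs follow from it, and the figures for 20 and 15 patients run straight on from it. At the 25% alternative the exact requirements (0.845, 0.89, 0.93) are close to the stated 0.83, 0.887 and 0.947, and the last of these is already conservative. The 62% case is uncommon at a 25% rate: exactly 4 responders occurs in about 8% of cohorts that reach stage 2. The outcome might also be meant as clinical benefit, which item 2 lists and for which a rate near 50% is plausible. Item 3 does not say that the analysis is per cohort, nor that the ROC alpha is two-sided. An exact one-sided 5% test would give about 88.5% with 7 responders and 74% with 4.

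Much of this bears on weight, and it supports a minor grading. It does not remove the conflict. Stating a condition does not make it consistent with the design rates given in the same section. Item 2 names clinical benefit separately and item 3 does not use the term. The 46% in section 2.2.6 carries no 12-week minimum, whereas item 2 requires stable disease beyond 12 weeks. Nothing says the cohorts are pooled for this analysis, and 27 is the cohort size. A one-sided test does not reproduce the stated 85%.

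Setting an exact 81% beside a Noether-based 85% also mixes methods. Like for like the loss is larger: 90% to 81% to 62% exact, or 84% to 74% to 56% by Noether.

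**Conclusion.** The concern holds and is minor. The arithmetic is correct for equal groups, but the design's response rates do not produce equal groups. At AUC 0.83 and 27 patients, exact power is about 81% with the 7 responders expected at a 25% rate and about 62% with the 4 that just pass a cohort. The shortfall against the stated 85% is modest at the alternative and large near the threshold. At 15 patients with 4 responders, the stated figure survives.

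These results rest on a two-sided 5% test, analysis within one cohort, radiographic response as the outcome, and an equal-variance normal shift. The primary analysis is unaffected.

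**What to change.** Revise section 9.3, item 3, in one of two ways.

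1. Keep radiographic response and restate power at the design's rates with exact or simulated rank-sum calculations. Suggested wording: *Per cohort, with a two-sided 5% rank-sum test, 85% power is reached for an AUC of about 0.845 with 7 responders of 27 and about 0.90 with 4 of 27; about 0.89 with 5 of 20; and about 0.93 with 4 of 15.* State the distributional assumption alongside.
2. If clinical benefit (CR, PR, or SD beyond 12 weeks) is the intended binary outcome, name it in item 3 and justify a rate of roughly 50%. The present AUCs can then stay.

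In either case, give the assumed responder share for 20 and 15 patients as well as for 27, say that the ROC alpha is two-sided, and say that the analysis is per cohort. The cost is a change of wording and, under the first option, a less favourable stated AUC for 27 patients. Sample size, data collection and the primary analysis do not change.
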